6.3 PER PROTOCOL

The Per Protocol (PP) Population is the subset of mITT who completed the follow-up study, and have data available at scheduled/unscheduled (within the allowable time window) visit. This population will be used as the for supportive efficacy and QoL analyses. Missing data will not be imputed.

6.4 ANALYSIS SUBSETS

- The Pediatric subset is defined as those subjects who received study medication (GS010 and sham treatment) who were less than 18 years old at the time of the Screening Visit in RESCUE or REVERSE Phase III studies. This population will be used for specific safety, efficacy and QoL analyses as deemed appropriate.
- Best eye and worst eye subsets of mITT and PP are based on the eye designation at baseline in RESCUE or REVERSE Phase III studies.
- On-chart LogMAR at baseline subsets are based on the baseline LogMAR in RESCUE or REVERSE Phase III studies.
- Subjects from the RESCUE Phase III study.
- Subjects from the REVERSE Phase III study.

7. INTERIM ANALYSES

Two interim analyses are planned at completion of Visit 3 (Year 3) and Visit 4 (Year 4), in addition to the final analysis at Year 5. The final results based on all time points will be included in the final Clinical Study Report (CSR).

No Data Monitoring Committee (DMC) will be assembled for evaluation of results in this long-term follow-up study.

8. STATISTICAL METHODS

All analyses will be performed on SAS Version 9.4 or higher.

Unless otherwise noted, categorical and binary variables will be summarized using counts and percentages. Percentages will be rounded to one decimal place.

Continuous variables will be summarized using the number of observations (n), mean, standard deviation (SD), median, first quartile (Q1), third quartile (Q3), minimum and maximum. Change from baseline or from nadir will also be summarized by a 95% confidence interval (CI).

Least square means, 95% CIs, and p-values will be reported from ANCOVA models. Estimated proportions with 95% CIs will be provided for Generalized Estimating Equation (GEE) models and for logistic regression models for responder endpoints. ANCOVA models will be run on all continuous endpoints, logistic regression for all subject responder endpoints, and GEE models for all eye responder endpoints.

Rounding rules are generally as follows:

- If the original variable has x decimal places, then minimum and maximum will be reported with x decimal places; mean, median, Q1, Q3, SD and CIs will be reported with x+1 decimal places.
- P-values will be reported with four decimal places.

Summary TFLs will display standard headers containing the sponsor name (“GenSight Biologics”) as well as a standard footer containing the name of the program used to generate the display, its path, and a date stamp. Headers, footers, titles, and column headers for tables will be repeated on every page of each display; pages will be numbered “Page x of y.” Visit labels in tables and figures will show visit name. Summary TFLs containing no applicable data will display a line reading, “No applicable data were reported” or similar wording. Dates and times will be presented using SAS DATE9. and SAS TIME5. formats.

8.1 SUBJECT DISPOSITION

The number and percentage of subjects, who were enrolled and who completed the study will be presented, together with the number and percentage of subjects who withdrew from the study prematurely and a breakdown of the corresponding reasons for withdrawal. These data will also be listed according to the eCRF. The number and percentage of subjects in the Safety, mITT, PP, and Pediatric Populations will also be presented.

Number of subjects who missed visits and the subjects who attended a particular visit will be presented. In addition, number of missing data for visual acuity and important SD-OCT parameters will also be summarized.

8.2 PROTOCOL DEVIATIONS AND VIOLATIONS

All protocol deviations will be listed. The decision regarding the major protocol deviations will be taken during the data review meeting.

8.3 DEMOGRAPHIC AND BASELINE CHARACTERISTICS

Demographic and baseline characteristics (gender, age, weight, height) will be summarized using descriptive statistics. Qualitative variables (gender) will be summarized using frequencies while quantitative variables (age, weight, height) will be summarized using mean, SD, median, Q1, Q3, minimum and maximum. These baseline demographic data will be imported from the RESCUE or REVERSE clinical database into the long-term follow-up clinical database.

Demographic and baseline characteristics will be summarized for the Safety Population. The analysis will be presented for RESCUE and REVERSE studies separately and pooled.

These data will also be listed based on the data listed in the eCRF.

Medical and surgical history data will be summarized by using counts and percentages and will be presented by system organ class and preferred term.

8.4 TREATMENTS

8.4.1 Extent of Study Drug Exposure

This study is the follow up of RESCUE/REVERSE studies where a single IVT injection was administered into the randomized eye and a single sham IVT injection in fellow eye on same day. Therefore, no summary table will be produced for the exposure data.

8.4.2 Concomitant Treatments

Prior and concomitant treatments will be coded using the World Health Organization dictionary (WHO Drug Dictionary current version). For each medical entity all Anatomical Therapeutic-Chemical (ATC) codes will be assigned according to the therapeutic classes to which the treatment belongs. Coding of treatments is detailed in the Coding Guidelines.

Prior and concomitant treatments will be summarized for the Safety Population by number and percentage of subjects of WHO Drug Dictionary ATC levels (ATC1, ATC2) and preferred term (PT). All prior and concomitant treatment data will be listed.

Concomitant medications from the RESCUE and REVERSE studies will be recorded as concomitant for those studies and those from the long-term follow-up study will be summarized separately. A combined summary of all concomitant medications will also be provided. Medications that span the original as well as the long-term follow-up study will be counted in both.

8.5 EFFICACY ANALYSES

All efficacy analysis will be conducted on the mITT Population, the PP Population, and additionally in subset populations as appropriate. All summaries will be performed on RESCUE separately, REVERSE separately, and on RESCUE and REVERSE combined.

8.5.1 Primary Efficacy Variable

Not applicable for this study.

8.5.2 Secondary Efficacy Variables

8.5.2.1 Pelli-Robson Contrast Sensitivity

Eye Level

Contrast Sensitivity will be summarized at each follow-up visit (Years 2, 3, 4, and 5), along with change from baseline to each follow-up visit.

This summary will be done comparing all-GS010 eyes to all-sham eyes.

These summary tables will be reproduced for eyes with on-chart LogCS at baseline, with off-chart LogCS at baseline (equivalence LogCS 0), and for all eyes.

The change of LogCS from baseline to the visit of interest will be compared between all-GS010 treated eyes and all-Sham treated eyes.

At each visit of interest, the following analyses related to Nadir LogCS will be performed:

- The change from Nadir LogCS will be calculated for each eye of each subject and will be expressed in LogCS.
- The time to Nadir LogCS will be calculated for each eye of each subject and will be expressed in Weeks.
- The mean LogCS change from Nadir will be assessed for all eyes, all GS010 eyes and all-Sham eyes.
- The mean time to Nadir LogCS will be assessed for all eyes, all GS010 eyes and all-Sham eyes.

Subject Level

At subject level, the best outcome (change from Baseline or change from Nadir) observed in either eye will be considered. The following summaries will be presented:

- The change of LogCS from baseline to the visit of interest
- The change of LogCS from Nadir to the visit of interest

8.5.2.2 LogMAR

Eye Level

Mean LogMAR BCVA will be summarized at each follow-up visit (Years 2, 2.5, 3, 4 and 5), along with mean change from baseline to each follow-up visit.

This summary comparing all-GS010 eyes to all-sham eyes will be repeated by comparing best-GS010 eyes to best-sham eyes and worst-GS010 eyes to worst-sham eyes.

These summary tables will be reproduced for those eyes with on-chart BCVA at baseline.

The curves of change from baseline at each time point for treated and sham eyes will be produced, with both sham and treated curves on same graph

The curves of absolute BCVA values at each time point for treated and sham eyes will be produced with both sham and treated curves on same graph.

LogMAR BCVA will be analyzed by using two approaches:

For the EMA, the change of LogMAR from baseline to the visit of interest will be compared between all-GS010 treated eyes and all-Sham treated eyes using a mixed-effects analysis of covariance (ANCOVA), with baseline LogMAR as a covariate, and subject and eyes of the subject as random factors.

The FDA has recommended comparing GS010 vs Sham in the Best-seeing eyes as a primary analysis. Therefore, change of LogMAR from baseline to the visit of interest will be compared between Best-GS010 treated eyes and Best-Sham treated eyes for the FDA. ANCOVA will be used for this analysis.

The EMA analysis is based on intra-subject comparison of change of LogMAR from baseline to the visit of interest. For FDA, the analysis is based on inter-subject comparison of change of LogMAR from baseline.

For eyes with on-chart BCVA at baseline, the change of LogMAR from baseline to the visit of interest will be analyzed between GS010-treated eyes and Sham-treated eyes.

At each visit of interest, the following analyses related to Nadir BCVA will be performed:

- The change from Nadir BCVA will be calculated for each eye of each subject and will be expressed in LogMAR.
- The time to Nadir BCVA will be calculated for each eye of each subject and will be expressed in Weeks.
- The mean LogMAR change from Nadir will be assessed for all eyes, all GS010 eyes and all sham eyes.
- The mean time to Nadir BCVA will be assessed for all eyes, all GS010 eyes and all sham eyes.

Subject Level

At subject level, the best outcome observed in either eye will be considered. The following summaries will be presented:

- The change of LogMAR BCVA from baseline to the visit of interest
- The change of LogMAR BCVA from nadir to the visit of interest

Analysis for European Medicines Agency (EMA)

The primary analysis will be performed on the mITT Population. The change from baseline to each follow-up visit in the LogMAR acuity will be the response. The change from baseline of all-GS010 eyes will be compared to the change from baseline of all-sham eyes applying a mixed-effects ANCOVA model using the following terms (or covariate) in the model:

- Subject as a random factor.
- The baseline LogMAR as a covariate.
- Treatment as a fixed effect.

The null and alternative hypotheses for the EMA LogMAR analysis are:

$$H_0: \mu_{\text{All-GS010}} = \mu_{\text{All-Sham}}$$

$$H_1: \mu_{\text{All-GS010}} \neq \mu_{\text{All-Sham}},$$

where μ presents the mean change from baseline to the visit of interest in LogMAR and “All” represents all eyes treated with GS010 or Sham.

The investigative site will not be included in the analysis as the number of subjects recruited per site will be very small. However, stratification by geographical area may be performed as a sensitivity analysis. Neighboring countries can be pooled to reach at least 9 subjects per geographical entity. The analysis will be performed using an alpha of 0.05 (two-sided test).

An additional model may add the treatment by geographical interaction (geographical areas: USA and Europe) to investigate the generalizability of the treatment effect. The following model diagnostics may be checked: normality of error terms, independence of error terms, independence of the covariate and treatment effect, and homogeneity of error variances.

Analysis for Food and Drug Administration

The primary analysis will be based on the mITT Population. The change from baseline of the best-GS010 treated eyes will be compared to the change from baseline of the best-sham eyes (inter-subject comparison) using an ANCOVA with baseline LogMAR as covariate. The analysis will be performed using an alpha of 0.05 (two-sided test). The statistical significance in favor of the best-GS010 treated eyes against the best-sham eyes will show evidence of the advantage of using GS010 for halting visual acuity loss or improving visual acuity in subjects with LHON. The difference in the mean change from baseline (adjusted mean difference) between the two treatment groups and associated 95% confidence interval will be reported.

The null and alternative hypotheses for the FDA LogMAR analysis are:

$$H_0: \mu_{\text{Best-GS010}} = \mu_{\text{Best-Sham}}$$

$$H_1: \mu_{\text{Best-GS010}} \neq \mu_{\text{Best-Sham}},$$

where μ presents the mean change from baseline to the visit of interest in LogMAR and “Best” represents the best-seeing eyes.

The following model diagnostics may be checked: linearity of regression, normality of error terms, independence of error terms, independence of the covariate and treatment effect, homogeneity of error variances, homogeneity of regression slopes.

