According to the EMA Committee for Medicinal Products for Human Use Guideline, entitled “Follow-Up of Patients Administered with Gene Therapy Medicinal Products,” and the United States Food and Drug Administration (US FDA) Center for Biologics Evaluation and Research Guidance for Industry (2006) entitled, “Gene Therapy Clinical Trials: Observing Subjects for Delayed Adverse Events,” viral vectors without integration, latency, or reactivation potential like AAV vectors present a low risk for gene therapy-related delayed adverse reactions. Although the FDA indicated that long-term follow-up is not considered necessary for this clinical development program, the EMA recommends a yearly monitoring plan up to 5 years post-treatment.

The regulatory intention of further observation is to determine the sustainability of efficacy, or whether declining efficacy after administration of gene therapy IMP occurs or whether more time is needed for tissue to be fully functional. For safety, the intention is to determine delayed-onset of adverse events (AEs), and to determine any additional unexplored long-term risks. The EMA refers to the Guideline (2008) entitled “Safety and Efficacy Follow-up: Risk Management of Advanced Therapy Medicinal Products” for possible delayed risks. One area for long-term observation is the potential risk directly related to the administration procedure of advanced therapies, and for this program would be the technique of IVT injection and any associated long-term effects.

In summary, all treated subjects in the RESCUE and REVERSE studies will be offered participation in the GS-LHON-CLIN06 study for the purpose of long-term safety evaluations, but only those providing informed consent and meeting eligibility criteria will be included in the study.

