5.2 BASELINE

The baseline value is defined as the last non-missing value prior to the start time of treatment administration in the RESCUE/REVERSE studies (Week 0). If assessment and treatment administration occur on same day and time is not captured, it will be considered as baseline.

For OCT parameters baseline is defined as the last non-missing value prior to the start time of treatment administration in the RESCUE/REVERSE studies (Week 0).

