5.3 CHANGE FROM BASELINE

The change from baseline value is defined as the value at a given time point minus the baseline value.

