Nadir of LogCS is defined for each eye of each subject as the worst LogCS observed from baseline to the visit of interest, including baseline and visit of interest values.

If contrast sensitivity is off-chart at any time point in the study, the first off-chart LogCS value will be considered to be the nadir, with the applied equivalence of LogCS 0.

BCVA and HVF

- Best-corrected visual acuity (BCVA), Humphrey Visual Field 30-2 (HVF) and Spectral Domain Optical Coherence Tomography (SD-OCT) will be assessed and then recorded on the eCRF.

Nadir of BCVA

The Nadir of BCVA is defined for each eye of each subject as the worst BCVA observed from baseline to the visit of interest, including baseline and visit of interest values. The first occurrence of this value will be considered as Nadir.

Responder Definitions

Eye Responder

- Definition 1: An improvement of at least 15 Early Treatment Diabetic Retinopathy Study (ETDRS) letters (equivalent to a decrease of at least 0.3 LogMAR) compared to baseline, or having a Snellen acuity equivalent better than 20/200 (equivalent to 1 LogMAR).
- Definition 2: Eyes that lose less than the 15 ETDRS letters (equivalent to an increase of less than 0.3 LogMAR) compared to baseline.

Subject Responder

- A subject will be considered a responder if the ETDRS score of the treated eye is at least 15 ETDRS letters better than the sham eye, or if the treated eye has a LogMAR acuity at least 0.3 LogMAR better than the sham eye, at a given visit (2, 2.5, 3, 4 and 5 years).

Vision Loss Duration at the Time of Treatment

- Vision loss duration in days will be based on the difference between the date of onset of vision loss of the first affected eye and baseline date (last BCVA non-missing value prior to the start time of treatment administration in the RESCUE/REVERSE studies).
- Vision loss duration will also be calculated for the second affected eye.

Treatment-Emergent Adverse Events (TEAE)

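### No planned analysis estimates change since Week 96/Year 2, so whether efficacy is sustained or declining gets no estimate with a confidence interval

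*SAP*

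**What the plan says.** **Purpose.** Protocol 5.3 says that regulators want further observation "to determine the sustainability of efficacy, or whether declining efficacy after administration of gene therapy IMP occurs", or whether function is still emerging. Protocol 6.2 makes long-term efficacy a secondary objective.

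**Reference point.** SAP 5.2 reads: "The baseline value is defined as the last non-missing value prior to the start time of treatment administration in the RESCUE/REVERSE studies (Week 0"). SAP 5.3 adds: "The change from baseline value is defined as the value at a given time point minus the baseline value". On that footing, SAP 8.5.2.2 states the EMA analysis as "the change of LogMAR from baseline to the visit of interest will be compared between all-GS010 treated eyes and all-Sham treated eyes" and the FDA analysis as "The change from baseline of the best-GS010 treated eyes will be compared to the change from baseline of the best-sham eyes". Changes in LogCS (8.5.2.1), SD-OCT (8.5.2.3), visual field (8.5.2.5) and quality of life (within 8.5.2.6), and the response in the exploratory MMRM (8.7.1), use the same baseline.

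**Responders.** In SAP 5.4, eye-responder Definition 1 needs a gain of at least 15 letters from baseline, or acuity better than 20/200 at the visit. Definition 2 is "Eyes that lose less than the 15 ETDRS letters (equivalent to an increase of less than 0.3 LogMAR) compared to baseline".

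**Analyses not tied to that baseline.** The SAP adds change from nadir and nadir-based responders, BCVA thresholds and on-chart status at each visit, and a treated-versus-sham subject responder with a randomization test. It also summarizes mean LogMAR and plots absolute BCVA at each visit (8.5.2.2, 8.5.2.4).

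**Time course.** The MMRM in Protocol 11.5.2.5 contains an interaction of linear time with treatment. SAP 8.7.1 lists three interactions with treatment (baseline LogMAR, time from disease onset, eye status) and none with visit or time. SAP 8.8 records the new covariance structure, the dropped random effect for eyes and the exploratory status of these models, but not this omission.

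**The concern.** Whether an effect lasts from Year 2 to Year 5 is a question about change over that interval. A change from pre-injection baseline answers a different one: whether the eye is still better or worse than before treatment. Suppose a GS010–sham difference is present at Year 2 and partly lost by Year 5. It can be significant against baseline at both visits, and a reader could take that as durability. The plan would supply no interval for what was lost.

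Safety reporting is not a reliable backstop, because worsening acuity that the investigator attributes to LHON progression is not an adverse event (Protocol 10.1.1, SAP 5.4).

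**Working it through.** The documents give no sample size, SD or expected effect, so there is no planned figure to reproduce. The check applies the SAP's own rules to assumed eye paths.

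**Inputs.** 15 letters = 0.3 LogMAR (SAP 5.4), so 1 letter = 0.02 (also Protocol 9.6.5); lower LogMAR is better. With B = baseline, Y2 and Y5 = the visit values:
- Definition 1 at Year 5: Y5 − B ≤ −0.30, or Y5 < 1.0.
- Definition 2 at Year 5: Y5 − B < +0.30.
- Nadir responder: Y5 − nadir ≤ −0.30, where nadir is the worst value up to and including the visit (taken here as the worst of the three shown).
- Letters lost since Year 2: (Y5 − Y2)/0.02.

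| B → Y2 → Y5 | Y5 − B | Y5 − Y2 | Letters lost since Y2 | Def. 1 | Def. 2 | Nadir −0.3 | BCVA ≤ 1 at Y2 / Y5 |
|---|---|---|---|---|---|---|---|
| 1.50 → 0.90 → 1.20 | −0.30 | +0.30 | 15 | yes | yes | yes | yes / no |
| 1.50 → 0.30 → 0.98 | −0.52 | +0.68 | 34 | yes | yes | yes | yes / yes |
| 1.30 → 1.00 → 1.58 | +0.28 | +0.58 | 29 | no | yes | no | yes / no |
| 1.30 → 1.00 → 1.60 | +0.30 | +0.60 | 30 | no | no | no | yes / no |

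In general, an eye that gained G letters by Year 2 can lose up to G + 14 and still meet Definition 2. If G ≥ 15 it can lose G − 15 and still meet the improvement limb of Definition 1; for G = 30 that is 15 letters, the first row. The last row shows that not every loss is masked.

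**The other analyses.**
- *Nadir.* Because nadir includes the current visit, change from nadir is never positive and cannot express net worsening. It does shrink between visits as an eye declines.
- *Visit thresholds.* BCVA ≤ 1 flags rows 1, 3 and 4 but not row 2. On-chart status (≤ 1.6) flags none of the four.
- *Between-eye responder.* Treated eye 0.80 → 1.30, sham eye 1.20 → 1.60: the gap goes from 0.40 to 0.30, so the subject still responds at Year 5 although the treated eye lost 0.50/0.02 = 25 letters.
- *Time course.* A model with treatment and visit but no interaction between them gives the same treatment difference at every visit, so it cannot show drift. SAP 8.7.1 promises estimates by visit, so an interaction may be intended, but it is not listed. Interacting treatment with time from onset does not clearly replace it: the protocol lists the two terms separately, and SAP 5.4 defines duration of vision loss only at the time of treatment.

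**Group level.** Let D2 and D5 be the GS010–sham differences in change from baseline. In subjects with both values, baseline cancels: (Y5 − B) − (Y2 − B) = Y5 − Y2. The contrast in change since Year 2 is therefore D5 − D2. With assumed D2 = −0.30 and D5 = −0.15, the Year 5 result still favours GS010 by 0.15, while D5 − D2 = +0.15 means that half the effect has gone. The interval needs Var(D5) + Var(D2) − 2Cov(D5, D2), and the covariance cannot be recovered from separate analyses by visit.

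**LOCF.** SAP 5.5.1 and 6.2 carry values forward. An eye with no value after Year 2 then has a change since Year 2 of exactly zero. If a fraction m of eyes is in that position and the others change by d on average, the LOCF mean is (1 − m)·d.

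**The case against.** A reader might infer that every efficacy comparison runs from the pre-injection baseline, or that this baseline is a mistake. The documents support neither. The visit thresholds, on-chart status, between-eye responder and absolute BCVA summaries use no baseline. The protocol specifies the RESCUE/REVERSE baselines (7.2.2), and anchoring there preserves the randomized contrast. The objective is efficacy up to 5 years post-treatment, and the GS010–sham contrasts at Years 2.5 to 5 are themselves new information. Scoring the first eye in the table as improved is also literally correct: it is 15 letters better than before injection.

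It is also fair that an average decline is not hidden. Mean LogMAR is tabulated and plotted at every visit, and with LOCF the same eyes contribute throughout, so the point estimate of mean change since Year 2 is a subtraction. Efficacy is secondary throughout (SAP 8.5.4).

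All of that stands. It leaves the subtraction without an interval and attenuated by LOCF, no count of eyes that lost vision during this study, and an unrecorded removal of the model term closest to a test of durability.

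**Conclusion.** The point holds as a missing supplementary analysis. The main comparisons are sound. No planned analysis measures change from Week 96/Year 2, so the question in Protocol 5.3 is not answered by any estimate with a confidence interval. At eye level, a 15-letter loss after Year 2 can coexist with response under both definitions, and the rules allow larger losses (34 letters in the second row). The visit thresholds and mean curves would show such declines in part.

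The eye paths and group differences are illustrations, not predictions. It would also go too far to say that a Year 2 reference would detect some particular small loss that the planned analyses would miss: the documents give neither subject numbers nor SDs from which to judge that. The change is worth making because the study's stated rationale includes the question and the data are already collected.

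**What to change.** Add to SAP 8.5.2.2, as a supplementary analysis for RESCUE, REVERSE and pooled:

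- **(a)** Change in LogMAR from Week 96/Year 2 to Years 3, 4 and 5 in GS010 eyes, in sham eyes and as the within-subject difference, each with a 95% CI, in mITT subjects with both values observed. State this as an explicit exception to the LOCF rule in 5.5.1 and 6.2, because LOCF pulls later change toward zero. The Week 96 fallback in 5.5.1 can supply the reference value when the Year 2 visit is missing.
- **(b)** Number and percentage of eyes losing at least 15 letters (0.3 LogMAR) since Year 2, by treatment.
- **(c)** Retention of response among Year 2 responders, labelled descriptive: selecting eyes on a good Year 2 value invites regression to the mean.
- **(d)** A treatment-by-visit (or time) term restored to the MMRM in 8.7.1, or its removal justified in 8.8.

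Base any statement on durability on (a). Label the analysis post hoc if data have already been reviewed. That may well apply, since interim analyses are planned at Years 3 and 4 and SAP 5.5.1 cites data-review listings bearing the SAP's own date.

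The cost is SAP wording and a few tables from existing data. The drawback is that subjects without both values drop out of (a), so the number excluded should be reported by visit.
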